Fenofibrate to prevent Ischemic
Cholangiopathy in Donation after Circulatory
Death liver transplantation (FICsDCD)

NCT05514119

28October2022

The FICsDCD Study

MEGA Award Protocol

Title of the study:	Fenofibrate to prevent Ischemic Cholangiopathy in Donation after Circulatory Death liver transplantation (FICsDCD)
Principal investigator:	[name]
Co-investigator(s):	[name], [name], [name]
Mentor:	[name]
Statistician:	[name]
IRB# or Activity#	22-007122

Abstract

Ischemic cholangiopathy (IC) is an early-onset, progressive bile duct stricturing syndrome occurring in 5-15% of transplanted livers, leading to biliary obstruction and allograft failure in up to 60% of cases. There is no definitive treatment for IC besides re-transplantation. The differential rate of IC drives the global preference for livers donated after brain death, over more abundant livers donated after circulatory death (DCD) that are prone to warm ischemia—the primary precipitant of IC. Any intervention to ameliorate IC will likely improve DCD organ utilization globally, thereby reducing transplant waitlist mortality and morbidity. Toxic bile acids (BA) in stagnant bile cause bile duct injury and stricturing, which may explain why stricturing progresses even after ischemia resolves at transplantation. Peroxisome proliferator-activated receptor (PPAR) agonists (such as the generic oral agent **fenofibrate**) potently down-regulate BA synthesis, promote BA excretion, and are safe and effective in other cholestatic diseases, but are not studied in transplant recipients. We hypothesize that fenofibrate could be safe, effective, cheap, and thus generalizable to impede the IC propagation. **In this prospective pilot study, we aim to evaluate 1) the tolerability and safety, 2) the efficacy of 12 weeks once-daily fenofibrate in reducing IC incidence after DCD liver transplantation, 3) assess the association between serum markers of cholestasis and development of IC.** Tolerability and safety will be assessed as proportions of: drug discontinuation, and new grade 3 or 4 adverse events. Efficacy will be assessed as incidence of cholangiographically-diagnosed IC and incidence of any IC-related complication.

Research Plan

Specific Aims

Specific Aim 1: To assess the tolerability and safety of 12 weeks once-daily fenofibrate (Lofibra) in a LT recipient population

Primary endpoint: Proportion of patients discontinuing fenofibrate due to adverse events

Secondary endpoints:

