- a. Proportion of patients with a new grade 3 or 4 adverse event.
- b. Proportion of patients with acute cellular rejection during fenofibrate treatment
- c. Mean change in calculated glomerular filtration rate (eGFR) from baseline during fenofibrate treatment weeks 4, 8, 12, and at 4 weeks after end of treatment
- d. Proportion of patients with myopathy confirmed by serum creatine kinase elevation at weeks 4, 8, 12, and at 4 weeks after end of treatment

The FICsDCD Study

Specific Aim 2: To assess IC incidence after 12 weeks of once-daily fenofibrate (Lofibra) in DCD LT recipients, compared with a historical, untreated control. Treatment and control populations will have an elevated predicted risk of IC, defined as alkaline phosphatase >2.5x upper limit of normal (ULN) at 21-60 days after LT.

Primary endpoint: IC incidence with 12 weeks fenofibrate versus a historical untreated cohort.

Secondary endpoints:

- a. Incidence of any IC-related complication at 12 weeks of fenofibrate treatment as a composite endpoint: biliary intervention (biliary stricture dilation, endoscopic biliary stent placement, percutaneous biliary drain placement), initiation of antimicrobial therapy for cholangitis or biloma, re-transplant evaluation due to IC, or death attributed to IC.
- b. Rate of alkaline phosphatase improvement to <1.67x ULN after 12 weeks fenofibrate.

Specific Aim 3: To assess the association between serum biomarkers and IC development.

Endpoints: Correlation of serum alkaline phosphatase, gamma glutamyl transferase, bile acids, fibroblast growth factor 19 (FGF19) and 7-alpha-hydroxy-4-cholesten-3-one (7AC4) levels at weeks 0, 4, 8, and 12 of treatment, with development of IC at 12 weeks of treatment.

II. Background and Significance

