IV. Research Design and Methods

Study design: A single-arm, open-label, prospective study of 12 weeks of fenofibrate (Lofibra) 160mg once daily in donation after circulatory death liver transplant recipients who have serum alkaline phosphatase $>2.5 \times$ ULN 21-60 days after transplantation, to determine fenofibrate tolerability, safety, and efficacy in preventing the ischemic cholangiopathy.

Treatment cohort: Recipients of DCD liver transplants at MCA or MCF

Historical cohort: DCD liver transplant recipients at MCA or MCF between 1/1/2016-6/1/2021

Diagnosis of IC: We will utilize previously-published diagnostic criteria for IC, defined as the occurrence of non-anastomotic biliary strictures in the absence of hepatic artery compromise¹

Inclusion criteria:

1. Female or male patients who have undergone DCD LT
2. At least one serum ALP level $>2.5 \times$ ULN between post-LT days 21-60 days (inclusive) after LT.

Exclusion criteria:

1. LT performed for primary sclerosing cholangitis or primary biliary cholangitis
2. Hepatic artery compromise (e.g thrombosis, stenosis), evaluated on abdominal doppler ultrasonography or angiography prior to enrollment..
3. Untreated biliary anastomotic (surgical) stricture or bile leak between days 0-60 after LT, evaluated during routine clinic examinations, labs, and abdominal ultrasonography.
4. Baseline GFR <30 ml/min
5. Previously known intolerance or allergy to fenofibrate
6. Other clinically significant comorbid condition, including psychiatric conditions, which in the opinion of the study team, may interfere with patient treatment, safety, assessment, or compliance with the treatment
7. Adults lacking capacity to consent to treatment

Interventions:

1. Consenting eligible patients will receive the fenofibrate formulation *Lofibra*, 160mg or renally-adjusted equivalent daily. Intended treatment duration of 12 weeks.
2. Post-transplant laboratory monitoring will be per standard Institutional protocol, at least weekly, through treatment period. Study laboratory monitoring will be done as below.

Analyses:

Specific Aim1:

- a. Tolerability: Proportion of patients who discontinue fenofibrate due to adverse event.
- b. Safety:
 - Proportion of patients with a new grade 3 or 4 adverse events based on CTCAE 5.0 Scale

The FICsDCD Study

- Proportion of patients with acute cellular rejection during fenofibrate treatment
- Mean change in eGFR from baseline at treatment weeks 4, 8, 12, and post-treatment week 4

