Potential Risks: Fenofibrate has been FDA-approved for dyslipidemia since 2004. The most common serious adverse events (SAEs) reported are elevated liver enzymes (3-13%), headache (3%), abdominal pain (5%), constipation (2%), nausea (2%), back pain (3%), CK elevation (3), and respiratory symptoms (2-6%). Fibrates are also associated with elevated serum creatinine, an important consideration in LT recipients who are concurrently exposed to other nephrotoxic agents and/or may have baseline renal impairment. In a large meta-analysis, mean creatinine increase was 0.37mg/dl, and GFR impact was minimal (2.7 ml/min). Moreover, both returned to baseline after drug cessation.¹² Fibrates are postulated to increase creatinine production, with direct nephrotoxicity occurring to a lesser degree. We will monitor participants with weekly labs and monthly and ad hoc study coordinator calls to determine SAEs. Patient reported intolerance or grade ≥ 3 SAEs (CTCAE 5.0 Scale) attributed to drug will be addressed with temporary or permanent drug discontinuation or dose reduction.

Protection: The primary aim of this study is to determine if the widely-used medication fenofibrate is tolerable and safe after LT, a unique population in which it has not been studied. Particular areas of interest are nephrotoxicity, hepatotoxicity, myotoxicity, and risk of allograft rejection. We use the standard, CTCAE 5.0 scale to determine severity of adverse events. The baseline safety and tolerability profile of fenofibrate is obtained from the FDA and post-marketing ('real world') data reported through LexiComp. As we are intervening early after transplantation, participants will be monitored intensively by the Transplant Program (twice weekly labs and at least twice-weekly transplant coordinator contact) in addition to Study staff.

The FICsDCD Study

Benefits: IC is among the most serious complications after LT. The proposed study of fenofibrate, a medication generally considered safe albeit not studied in a LT population, may facilitate further study of this agent as a low risk, low cost, intervention to impede the development of IC and its downstream complications including frequent biliary intervention, hospitalization, loss of functional capacity, allograft failure, and need for re-transplantation.

VI. Gender/Minority Mix There are no known gender or racial disparities in IC. All eligible, consecutive LT recipients irrespective of gender or race will be offered study enrolment.

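### Intolerance may be managed by dose reduction, but the tolerability endpoint counts only discontinuation and no other Aim 1 endpoint counts dose reductions

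*Combined protocol and SAP*

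**What the plan says.** Specific Aim 1 concerns the tolerability and safety of 12 weeks of once-daily fenofibrate, which the protocol names as its primary aim. The primary endpoint is "Proportion of patients discontinuing fenofibrate due to adverse events". The Analyses part of section IV repeats it: "Tolerability: Proportion of patients who discontinue fenofibrate due to adverse event". The Abstract likewise describes tolerability and safety through drug discontinuation and new grade 3 or 4 events.

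The secondary endpoints of Aim 1 are:
- (a) "Proportion of patients with a new grade 3 or 4 adverse event";
- (b) the proportion with acute cellular rejection;
- (c) "Mean change in calculated glomerular filtration rate (eGFR) from baseline during fenofibrate treatment" and 4 weeks after it;
- (d) the proportion with myopathy confirmed by raised creatine kinase (CK).

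Management of intolerance is described in section V, Potential Risks. There are two triggers: "Patient reported intolerance", with no grade attached, and events of grade 3 or higher attributed to the drug. Either "will be addressed with temporary or permanent drug discontinuation or dose reduction".

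The dose under Interventions in section IV is "160mg or renally-adjusted equivalent daily", so a lower starting dose for reduced renal function is planned treatment. The Schedule of Events includes tolerability and safety assessments weekly in weeks 0-4, once in each of the two later treatment periods, and once after treatment.

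**The concern.** The management rule offers three responses to intolerance: a temporary stop, a permanent stop or a lower dose. The tolerability endpoint is built on stopping only. A patient whose intolerance is handled by the third response leaves no mark on that endpoint, although the patient did not stay on the intended dose.

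At stake is how the primary aim can be read. The protocol presents this as the first safety and tolerability analysis of fenofibrate in liver transplant recipients. It expects the result to bear on prophylaxis after transplantation for PBC and PSC and, if there is an efficacy signal, to lead to a randomized trial. Both uses need to know whether recipients completed 12 weeks at the intended dose or only at a dose cut for an adverse event. The planned results do not separate the two.

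**Working it through.** **Step 1. Is a dose reduction for an adverse event counted anywhere in Aim 1?** Take a patient whose dose is cut for an adverse event and who never stops the drug.

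| Aim 1 endpoint | What it records for this patient |
|---|---|
| Primary: discontinuation due to adverse event | Nothing |
| (a) New grade 3 or 4 event | The event, if grade 3 or 4; not the dose cut |
| (b) Acute cellular rejection | The rejection, if that was the event; not the dose cut |
| (c) Mean eGFR change | A contribution to a mean; no patient is counted |
| (d) CK-confirmed myopathy | The myopathy, if that was the event; not the dose cut |

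No row counts the dose reduction. If the event is below grade 3 and is not rejection, CK-confirmed myopathy or an eGFR change, the patient may appear in no Aim 1 proportion. Such a patient can exist under the plan, because the intolerance trigger carries no grade limit.

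**Step 2. Inputs for the size.** The treatment arm is n = 32 (section V, Population). Aim 1 has no sample size, precision target or threshold of its own, so there is no plan figure to reproduce. The only sample-size calculation belongs to the Aim 2 comparison of cholangiopathy incidence and is not affected. The documents give no expected number of dose reductions, so the counts below are assumptions. All 32 patients are taken as the denominator, and no patient is assumed to discontinue.

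**Step 3. Weight of one patient.** 1/32 = 0.03125, or 3.1 percentage points.

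**Step 4. Exact (Clopper-Pearson) 95% limits** for x of n = 32: the lower limit is the 2.5% quantile of Beta(x, n − x + 1), or 0 when x = 0. The upper limit is the 97.5% quantile of Beta(x + 1, n − x). For x = 0 the upper limit is 1 − 0.025^(1/32) = 0.109.

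| Assumed patients with dose reduction only | Primary endpoint (discontinuation) | Discontinuation or dose reduction |
|---|---|---|
| 0 | 0/32 = 0% (0-10.9%) | 0/32 = 0% (0-10.9%) |
| 2 | 0/32 = 0% (0-10.9%) | 2/32 = 6.3% (0.8-20.8%) |
| 5 | 0/32 = 0% (0-10.9%) | 5/32 = 15.6% (5.3-32.8%) |

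The primary endpoint is the same in every row. At zero dose reductions the two measures agree and nothing is lost.

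**The case against.** The strongest reply is that the plan contains no error. Potential Risks describes patient care, and Specific Aim 1 defines an endpoint. Discontinuation due to adverse events is a legitimate tolerability endpoint, and a reader told that x of 32 discontinued learns exactly that. No hypothesis test, threshold or go/no-go rule rests on the proportion. Tolerability assessments, coordinator calls and record review are already planned, so dose changes could be found and reported anyway. All of this stands, and it limits the point to a reporting improvement. It does not remove the point: nothing commits the investigators to reporting dose reductions, and a definition chosen after seeing open-label, single-arm data is weaker than one fixed beforehand.

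Three stronger readings are tempting, and the documents do not support them.

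- A reader might infer that the plan labels dose-reduced patients as having tolerated the drug. It has no such category. It only leaves them out of the numerator.
- A reader might take the adverse event rates under Potential Risks and derive an expected number of dose-reduced patients. The protocol introduces those rates as serious adverse events, gives no CTCAE grades, does not present them as rates in transplant recipients (it says fibrates have not been studied in any transplant population), and does not say what share would lead to a dose cut. If many were grade 3 or 4, secondary endpoint (a) would show the events. No expected count follows.
- A reader might infer that every lower dose is a hidden intolerance. The renally adjusted starting dose is planned treatment and is not. A dose cut on treatment for a drug-attributed renal event is different: nephrotoxicity is a named area of interest, and a mean eGFR change does not count the patients affected.

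**Conclusion.** The point holds as a minor one. Following the plan exactly can give 0% on the primary tolerability endpoint while some recipients stayed on fenofibrate only at a dose reduced for an adverse event, and no other Aim 1 endpoint would show the reduction. The size is 3.1 percentage points per patient. Over the illustrated range of 0 to 5 patients, the gap between the two measures runs from nothing to 15.6 points. That range rests on assumed counts, a denominator of 32 and no discontinuations. It is not a forecast, and zero is possible. The reading of the endpoints themselves needs no assumption.

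**What to change.** Leave the primary endpoint and patient management as they are. Add one secondary tolerability endpoint to Specific Aim 1 and to the matching Analyses item: the proportion of patients with discontinuation (temporary or permanent) or dose reduction due to an adverse event during the 12 weeks, with an exact 95% CI. State beside it the number with dose reduction only. Further splits by grade or duration are not worthwhile with 32 patients.

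Include on-treatment dose cuts made for a drug-attributed renal adverse event. Exclude only the planned renally adjusted starting dose.

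Record the action and its reason in REDCap at the tolerability assessments already in the Schedule of Events.

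The cost is one endpoint line and one added data item, with no extra visit, sample or patient and no change to the sample size. The downside is a second, less favourable figure beside the primary endpoint.
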